## **6.2 Control Device**

All study subjects that are part of Cohort 2 (cemented) concurrent control group will receive the Triathlon Cemented Tibial Baseplate, Triathlon Cemented Patella, Triathlon CR or PS Cemented Femoral Component, and Triathlon Tibial Inserts. The Triathlon Total Knee System components have been cleared in the United States under the following 510(k) numbers: Triathlon Cemented Femur (K042993), Tibial Inserts (K051146 and K050539), Triathlon Tibial Baseplate (K031729), Triathlon Patella (K040267). These components are intended for cemented application. Appendix I provides a listing of all protocol-specified components.

The Triathlon Cemented Tibial Baseplate is fabricated from cast cobalt-chromium-molybdenum alloy. The Triathlon Cemented Tibial Baseplate is neutral in configuration, and is available in eight proportional sizes. The undersurface of the tibial tray and the keel is grit blasted for interdigitation with polymethylacrylate (PMMA) bone cement. The keel of the tibial tray is designed with normalizations for rotational stability and cement interdigitation. The superior aspect of the tibial tray has a rim that contains tabs that mate with the outer periphery of the tibial insert, along with the locking wire used on the tibial insert. This locking feature is designed to provide secure attachment of the tibial insert to the tray, and is designed to reduce micromotion of the tibial insert on the tray.

The Triathlon Cemented Patella components are available in two styles, symmetric and asymmetric. Both are fabricated from either N2VAC UHMWPE or X3 UHMWPE. The symmetric design is available in six diameters (27 mm, 29 mm, 31 mm, 33 mm, 36 mm, and 39 mm) and four thicknesses (8 mm, 9 mm, 10 mm, and 11 mm). The symmetric design features a central cement recess, and three pegs on the bone interface surface. The Triathlon Symmetric

CONFIDENTIAL

This material is the property of Stryker Orthopaedics. Do not disclose or use except as authorized in writing by Stryker.

Patellar component is intended to be implanted via a resurfacing or inset surgical technique. The asymmetric design features a flare in the lateral aspect of the component. The asymmetric patellar component also has a central recess with three pegs for cement fixation.

The Triathlon Cemented Femur is fabricated from cast cobalt-chromium-molybdenum alloy, and is intended for cemented application to replace the articulating surface of the distal femur. It is available in right and left configurations, and eight proportional sizes (sizes 1 to 8) to accommodate differences in patient anatomy. The interior surface of the component is grit-blasted to increase the surface roughness – this is intended to promote interdigitation of the PMMA bone cement with the surface texture and the apposing bone.

### **6.3 Device Retrieval Process**

Stryker Orthopaedics will retrieve the Triathlon Tritanium Tibial Baseplate and/or Patella and/or adjacent tissues for analysis to help characterize potential device-related complications. In the event that the Triathlon Tritanium Tibial Baseplate and/or Patella are removed from a study subject, the procedure outlined in the Retrieved Implant Analysis Protocol (Appendix C) should be followed. In addition:

1. When revision of a study subject is scheduled, the study coordinator (SC) should contact the Clinical Study Manager (CSM) or other Stryker Clinical Research personnel assigned to the project, as soon as possible.
2. Stryker Clinical Research will send a retrieval container to the SC.
3. After the device is explanted, the SC or an identified Stryker field representative will retrieve the device and place it in the retrieval container, following the instructions in Appendix C.
4. The SC, an identified field representative or Stryker Clinical Research will complete a Product Experience Report (PER).
5. If not completed by Stryker Clinical Research, the PER should be faxed or emailed to Stryker Product Surveillance at [contact] or [[contact]](mailto:[contact]), as well as to Stryker Clinical Research at [contact] or to the Clinical Research email addresses listed on the Sponsor Contact Sheet.
6. The PER should be attached to the retrieval container and sent to Product Surveillance. A de-identified operative report should be included, when available.

CONFIDENTIAL

This material is the property of Stryker Orthopaedics. Do not disclose or use except as authorized in writing by Stryker.

7. Stryker Clinical Research will follow up with Product Surveillance to obtain a PER number.
8. A summary of results will be provided to the investigator upon his/her request.

## 7 Evaluations

### 7.1 Preoperative Visit

During the preoperative visit, patients that are possible candidates for this study are screened to determine if they meet the inclusion/exclusion criteria. If the patient is a candidate, the investigator proposes participation in the study to the patient, according to GCP guidelines. Patients must sign an IRB/EC approved Informed Patient Consent Form prior to participating in any study related activities. Consent must be obtained within 4 months prior to surgery. In the event a subject does not have surgery, Stryker should be contacted to discuss if/when the surgery will be rescheduled. If the surgery is rescheduled more than 4 months from the date of preoperative data collection, the subject will need to be re-consented, all preoperative data will need to be re-collected and all original preoperative data will need to be removed from the database.

Once the patient has been consented, preoperative data will be collected including: demographics and medical history, 2011 KSS, OKS, SF-12, AP, ML and Merchant radiographs for both Cohort 1 (cementless) and Cohort 2 (cemented).

All preoperative data must be collected within 4 months prior to the scheduled date of surgery, with the exception of radiographs, acceptable within 1-year prior to the scheduled date of surgery. All information collected preoperatively will be used to quantify the sample population and compare postoperative progress. In the event a subject does not have surgery, Stryker should be contacted to discuss if/when the surgery will be rescheduled. If the surgery is rescheduled more than 4 months from the date of preoperative data collection, the subject will need to be re-consented, as noted above.

CONFIDENTIAL

This material is the property of Stryker Orthopaedics. Do not disclose or use except as authorized in writing by Stryker.

## **7.2 Surgery**

Surgical details will be collected from the operative notes and at the time of surgery for both Cohort 1 (cementless) and Cohort 2 (cemented).

## **7.3 6-week Visit**

During the 6-week visit ( $\pm$  3 weeks), the following evaluations will be collected: 2011 KSS, OKS, SF-12, AP, ML and Merchant radiographs for both Cohort 1 (cementless) and Cohort 2 (cemented).

## **7.4 6-month Visit**

During the 6-month visit (- 14 - + 4 weeks), the following data will be collected: 2011 KSS, AP, ML and Merchant radiographs for both Cohort 1 (cementless) and Cohort 2 (cemented).

## **7.5 Annual Follow-up Visits**

### **7.5.1 Cohort 1 (cementless) Annual Follow-up Visits**

Cohort 1 (cementless) will be followed to 10 years postoperatively according to the following schedule. Clinical data will be collected via office visit by the investigator at the following annual postoperative intervals: 1-year, 2-year 5-year and 10-year. Tools for postoperative evaluation at each of these intervals will be the 2011 KSS, OKS, SF-12, AP, ML and Merchant radiographs. In the event that an in-person visit cannot be conducted and radiographs cannot be obtained, a Follow-up Questionnaire will be completed via mail, online completion (if available), or subject telephone interview with the subject by investigative site personnel.

The Follow-up Questionnaire, OKS and SF-12 will also be collected at the 3-year, 4-year, 6-year, 7-year, 8-year and 9-year intervals via mail, online completion (if available), or subject telephone interview with the subject by investigative site personnel. The questionnaire is used to obtain information on satisfaction, pain, complications and any study device revisions to enable calculation of the Kaplan-Meier Survival Curves.

All clinical data, radiographs, and patient outcomes data must be collected within  $\pm$  2 months of the 1-year and 2-year anniversary dates. For remaining annual time points, the window expands to  $\pm$  3 months of the 3-year anniversary date and  $\pm$  4 months of the 4-year through

CONFIDENTIAL

This material is the property of Stryker Orthopaedics. Do not disclose or use except as authorized in writing by Stryker.

10-year anniversary dates.

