### **2.1.2 Secondary**

The secondary objectives of this study are:

- To assess the Kaplan-Meier survival curves of the Triathlon Tritanium Tibial Baseplate and Triathlon Tritanium Patella and compare them with those reported for cemented knee components in the literature. The overall revision rate will evaluate all-cause revision and removal rates of the Triathlon Tritanium Tibial Baseplate and Triathlon Tritanium Patella.
- To compare 2011 KSS scores, SF-12 scores, and OKS scores between Cohort 1 (cementless) and Cohort 2 (cemented) at 2 years postoperative.

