#### **Patient Reported Outcomes:**

Pain, function and health related QOL will be evaluated for both cohorts according to their respective evaluation schedules with the SF-12, OKS and patient derived 2011 KSS components. The SF-12 is a 12 item patient self-assessment evaluating health and general well being. The OKS is a 12 item patient reported outcome questionnaire that evaluates function and pain after total knee arthroplasty. The 2011 KSS subjective component is a patient reported outcome measure based on satisfaction with outcome, fulfillment of expectations and ability to perform functional activities.

CONFIDENTIAL

This material is the property of Stryker Orthopaedics. Do not disclose or use except as authorized in writing by Stryker.

A Follow-up Questionnaire is administered annually for both cohorts according to their respective evaluation schedules to assess for patient satisfaction, pain, study device survivorship and to capture AEs. This questionnaire provides the information necessary to create an accurate Kaplan-Meier Survival Curve.

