### **7.5.2 Cohort 2 (cemented) Annual Follow-up Visits**

Cohort 2 (cemented) will be followed to 5 years postoperatively according to the following schedule. Clinical data will be collected via office visit by the investigator at the following annual postoperative intervals: 1-year, 2-year and 5-year. Tools for postoperative evaluation at each of these intervals will be the 2011 KSS, OKS, SF-12, AP, ML and Merchant radiographs. In the event that an in-person visit cannot be conducted and radiographs cannot be obtained, a Follow-up Questionnaire will be completed via mail, online completion (if available), or subject telephone interview with the subject by investigative site personnel.

The Follow-up Questionnaire, OKS and SF-12 will also be collected at the 3-year and 4-year intervals via mail, online completion (if available), or subject telephone interview with the subject by investigative site personnel. The questionnaire is used to obtain information on satisfaction, pain, complications and any study device revisions to enable calculation of the Kaplan-Meier Survival Curves.

All clinical data, radiographs, and patient outcomes data must be collected within  $\pm$  2 months of the 1-year and 2-year anniversary dates. For remaining annual time points, the window expands to  $\pm$  3 months of the 3-year anniversary date and  $\pm$  4 months of the 4-year and 5-year anniversary dates.

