## **9.3 Missing Data**

Missing data in OKS will be imputed when calculating the OKS score using the method recommended by the new OKS scoring system. Missing data in 2011 KSS will be imputed when calculating KSS scores with the method recommended in the user manual of the 2011 Knee Society knee scoring system. No other missing data will be imputed.

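### The remote fallback for a missed 2-year office visit does not name the OKS or SF-12, although both are collected remotely in other years

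*Combined protocol and SAP*

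**What the plan says.** For the office visits, which include year 2, section 7.5.1 lists the instruments: "Tools for postoperative evaluation at each of these intervals will be the 2011 KSS, OKS, SF-12, AP, ML and Merchant radiographs". Section 7.5.2 does the same for Cohort 2 at years 1, 2 and 5. Both sections then give the same fallback: "In the event that an in-person visit cannot be conducted and radiographs cannot be obtained, a Follow-up Questionnaire will be completed via mail", or online, or by a telephone interview. No other instrument is named for that contact.

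The next paragraph of each section shows that remote collection of the two patient-reported scores is already part of the plan. In Cohort 1: "The Follow-up Questionnaire, OKS and SF-12 will also be collected at the 3-year, 4-year, 6-year, 7-year, 8-year and 9-year intervals via mail". In Cohort 2: "The Follow-up Questionnaire, OKS and SF-12 will also be collected at the 3-year and 4-year intervals via mail". The online and telephone routes are offered there too.

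The between-cohort objective in section 2.1.2 is fixed at year 2: "To compare 2011 KSS scores, SF-12 scores, and OKS scores between Cohort 1 (cementless) and Cohort 2 (cemented) at 2 years postoperative". Section 9.3 provides imputation when an OKS or a 2011 KSS score is being calculated, and then states: "No other missing data will be imputed". Section 9.4.4 restricts the efficacy analyses to subjects who can be evaluated for efficacy.

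Both evaluation schedules mark the OKS and SF-12 at 2 years as mandatory for every case and do not say how they must be collected. The Follow-up Questionnaire appears in those schedules only from year 3 onward, so the form named as the year-2 substitute is not on the year-2 schedule.

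**The concern.** The protocol names all three forms when it wants all three by remote contact. In the fallback it names one. A coordinator who reads section 7.5.1 or 7.5.2 literally will telephone or write to an absent patient at 2 years, complete the Follow-up Questionnaire and stop. That questionnaire cannot supply the missing scores; its purpose is different: "The questionnaire is used to obtain information on satisfaction, pain, complications and any study device revisions".

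The OKS and SF-12 need no clinic visit. On the first, section 2.1.3 says: "The OKS is a 12 item patient reported outcome questionnaire that evaluates function and pain after total knee arthroplasty". It describes the SF-12 as a 12-item self-assessment. The missing scores would therefore be avoidable.

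What is at stake is the 2-year comparison of cementless with cemented cases, the stated reason for enrolling the 144 control cases (section 9.4.2). Patients who cannot attend but do answer are unlikely to be a random subset. The cohorts are not randomized, a center may join only one arm (section 3.2.1), and Cohort 2 enrolls after Cohort 1 (section 3.3), so attendance could differ between them. The same gap affects year 10, where section 9.4.1 plans a paired test against the preoperative scores in Cohort 1.

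**Working it through.** **The plan's own figure.** The only sample-size calculation (section 9.4.2) is for the primary endpoint. A one-sample normal approximation with the variance at 99% gives 0.99 × 0.01 × (1.645 + 1.645)² / 0.02² = 267.85, against 267 stated. Then 267 / 0.85 = 314.1, which rounds up to the stated 315. So the 15% is a loss-to-follow-up allowance for the primary endpoint. No effect size, SD, power or attrition is given for the 2-year score comparison.

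**Can a year-3 score stand in?** No. By sections 7.5.1 and 7.5.2 the 2-year window closes at 24 + 2 = 26 months and the 3-year window opens at 36 − 3 = 33 months.

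**Does another rule fill the gap?** I read the imputation in section 9.3 as completing a partly answered OKS or KSS. A form that was never sent has nothing to complete, and the SF-12 has no rule at all.

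**Size of the precision effect.** Inputs from section 9.4.2: 356 and 144 cases. Assumptions, none of them in the documents as attendance rates:

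- 15% truly lost in both cohorts: 356 × 0.85 = 302.6 and 144 × 0.85 = 122.4 remain.
- A further share f of those, 5% to 15%, miss the office visit but can be reached.
- Two-sided 5% test, 80% power, difference in SD units: detectable difference = (1.960 + 0.842) × √(1/n₁ + 1/n₂).

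| f | Recoverable, Cohort 1 | Recoverable, Cohort 2 | Cases with a score if not recovered | Detectable difference |
|---|---|---|---|---|
| 0 (all recovered) | – | – | 303 v 122 | 0.300 SD |
| 5% | 302.6 × 0.05 = 15.1 | 122.4 × 0.05 = 6.1 | 287 v 116 | 0.308 SD |
| 10% | 30.3 | 12.2 | 272 v 110 | 0.316 SD |
| 15% | 45.4 | 18.4 | 257 v 104 | 0.326 SD |

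**Size of a possible bias.** If a share m of a cohort has no score and those patients differ by d SD from the rest, the observed mean shifts by m × d. With the same d in both cohorts, the between-cohort shift is (m₁ − m₂) × d. For illustration, 15% v 5% gives 0.10 × 0.3 = 0.03 SD or 0.10 × 0.5 = 0.05 SD. With equal shares and equal d it cancels. The documents give no value for m₁, m₂ or d.

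**The case against.** The strongest reply is that the protocol does not waive the scores. The schedules require the OKS and SF-12 at 2 years without fixing a mode, and sections 7.5.1 and 7.5.2 require patient outcomes data within two months either side of the anniversary. Section 11.4 requires missing data to be explained, and no text forbids posting the forms. A site could comply in full. This stands: a reader might infer that the scores are certain to be lost whenever a visit is missed, and the documents do not support that. They support something narrower: a required score, and a fallback that omits it, so that practice may vary by center.

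A reader might also take the plan's 15% as the pool of patients from whom scores could be recovered. That does not work. Section 10.3 calls a subject lost only after three logged calls and certified mail go unanswered, so those patients are the ones who cannot be reached. The relevant group is absent but responsive, and its size is not stated.

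Third, the comparison is one secondary objective without a stated margin or power, the fallback is worded identically in both cohorts, and no evidence of differential attendance is given. Contact efforts (section 10.3), visit reimbursement (section 15.3) and the optional retention program (Appendix H) should reduce missed visits. All of this limits the size of the problem. None of it supplies an OKS or SF-12 for a patient who stays away.

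**Conclusion.** The point holds as a gap in a stated rule. Sections 7.5.1 and 7.5.2 name only the Follow-up Questionnaire when an office visit fails, and no other section provides remote OKS or SF-12 collection at 2 years. A site that does exactly what the fallback says will have no score for a patient it reached, at the between-cohort time point.

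The effect is small to moderate. Under the assumptions of 15% truly lost and a further 5–15% absent but reachable, about 15–45 Cohort 1 and 6–18 Cohort 2 scores are recoverable, and the detectable difference is about 0.30 SD rather than 0.31–0.33 SD. The stronger reason to act is selective missingness in a non-randomized comparison. Its direction and size cannot be established from the documents, and it would be near zero if the two cohorts lost similar patients at similar rates.

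The primary endpoint is little affected, because the Follow-up Questionnaire captures revisions. The case for changing the rule rests on its low cost.

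**What to change.** In sections 7.5.1 and 7.5.2, state that the remote contact replacing a missed office visit at year 1, 2, 5 or (Cohort 1) 10 collects the OKS and SF-12 together with the Follow-up Questionnaire, within the same visit window, and that the mode of collection is recorded. Add a matching footnote to both evaluation schedules, since the questionnaire is not listed there at years 1 and 2.

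The patient-completed sections of the 2011 KSS could be added as an option. A reader might assume this is equally free, but the protocol collects the KSS only at visits. Remote KSS would be a new procedure and would need a rule for a score without its surgeon-completed section. The OKS and SF-12 alone close the main gap.

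Cost: one sentence in each of two sections and the schedule notes. The OKS and SF-12 forms and remote routes are already in use from year 3. The downside is a few more pages for the patient and some scores collected by a different mode from the rest.

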### **7.5.2 Cohort 2 (cemented) Annual Follow-up Visits**

Cohort 2 (cemented) will be followed to 5 years postoperatively according to the following schedule. Clinical data will be collected via office visit by the investigator at the following annual postoperative intervals: 1-year, 2-year and 5-year. Tools for postoperative evaluation at each of these intervals will be the 2011 KSS, OKS, SF-12, AP, ML and Merchant radiographs. In the event that an in-person visit cannot be conducted and radiographs cannot be obtained, a Follow-up Questionnaire will be completed via mail, online completion (if available), or subject telephone interview with the subject by investigative site personnel.

The Follow-up Questionnaire, OKS and SF-12 will also be collected at the 3-year and 4-year intervals via mail, online completion (if available), or subject telephone interview with the subject by investigative site personnel. The questionnaire is used to obtain information on satisfaction, pain, complications and any study device revisions to enable calculation of the Kaplan-Meier Survival Curves.

All clinical data, radiographs, and patient outcomes data must be collected within  $\pm$  2 months of the 1-year and 2-year anniversary dates. For remaining annual time points, the window expands to  $\pm$  3 months of the 3-year anniversary date and  $\pm$  4 months of the 4-year and 5-year anniversary dates.

## **8 Adverse Events**

### **8.1 Reporting of Adverse Events**

The AE reporting requirements for this study are as follows:

- All AEs that are operative site related, regardless of seriousness or time of occurrence.
- All AEs that meet the definition of serious and occur within the perioperative period (intraoperative to hospital discharge)

CONFIDENTIAL

[figure not shown]
This material is the property of Stryker Orthopaedics. Do not disclose or use except as authorized in writing by Stryker.

On postoperative functional evaluations, investigators and SCs are prompted to question subjects as to whether they have seen a doctor for any reason, been hospitalized for any reason or have a current impediment to their function.

Additionally, SCs are responsible for following up with the subjects regarding any questionable responses received on the Follow-up Questionnaire. If it is determined upon this further investigation that a protocol-defined AE has occurred, the SC will be responsible for completing an AE eCRF, submitting the event to Stryker and reporting to the IRB/EC, as required.

The following decision tree facilitates identification of AEs for which reporting is required under this study protocol:

Figure 2: Adverse Event Decision Tree

CONFIDENTIAL

This material is the property of Stryker Orthopaedics. Do not disclose or use except as authorized in writing by Stryker.

### ***General Physical Examination Findings***

At screening for inclusion into the study, any clinically significant abnormality should be recorded as a preexisting condition and reported on the Demographics eCRF. From the time of consent forward, any new clinically significant findings or abnormalities that meet the definition of a protocol defined AE must also be recorded and documented as an AE.

